11.2 Sample Size and Power Calculations

We calculated the least rVE that is detectable with 80% power in a 3-year study for several aims. As described in Section 11.1, we plan to test the null hypothesis that Flublok is not any more effective than the comparator (i.e., a superiority test), using a 2-sided test, $p < 0.05$. Our allocation

ratio of 1:1 implies that each year, KPNC would give Flublok Quadrivalent vaccine to 400,000 members aged 18–64 years, and SD-IIV to another 400,000 similar KPNC members.

Each row of the tables in the Appendices (**Section 15**) shows power for a possible scenario for a given outcome and a specific age range. The expected incidence of the outcome in vaccinees who received SD-IIV (based on incidence observed in the 2016–2017 influenza season) is in column 4; the relative risk (estimated by the relative hazard ratio) associated with getting Flublok Quadrivalent vaccine versus a comparator is in column 5; the corresponding rVE in column 6; and the power in the last column. These power calculations estimate our power to test the null hypothesis that Flublok Quadrivalent vaccine VE does not differ from SD-IIV(s).

Because the comparison group will not be unvaccinated—they are getting SD-IIV—we will be estimating and testing rVE: i.e., the percent reduction in the incidence of “breakthrough cases” (e.g., influenza episodes in vaccinees) that results from the use of Flublok Quadrivalent vaccine rather than the SD-IIV vaccines.

As an example, for the outcome of PCR-confirmed flu diagnosis, the first row of the first table indicates that power is very high (>0.99) to detect a rVE of 0.30 (which amounts to a 30% rVE) in a 3-year study of vaccinees aged 18–64 years, assuming that influenza incidence in the comparator arm will be the same as it was in the 2016–2017 influenza season. Comparing rows 5 and 6 of the first table, our power to detect a rVE of 10% rather than 5% against test-positive influenza in those aged 18–64 years increases to 0.96 from 0.45.

Depending on priorities and data availability, we may potentially conduct subgroup analyses of rVE, including the subgroups defined by:

- influenza type A and B
- selected diagnoses or conditions (e.g., in 50–64 year olds, rVE of those with specified comorbid conditions, such as cardiac, pulmonary, and metabolic comorbidities)
- time periods and/or time-since-vaccination within a season
- specific comparator SD-IIV(s) (if more than one comparator is used)

12 Ethical and Legal Issues and Investigator / Sponsor Responsibilities

12.1 Ethical Conduct of the Study / Good Clinical Practice

The conduct of this study will be consistent with the standards established by the Declaration of Helsinki and compliant with the ICH guidelines for GCP as well as with all local and / or national regulations and directives.

12.2 Source Data and Source Documents

The source data are stored in the KPNC EMR.

12.3 Confidentiality of Data and Access to Subject Records

Prior to initiation of the study, the Investigator will sign a fully executed agreement, including confidentiality, with Sanofi Pasteur. Sanofi Pasteur personnel (or designates) will not have any access to subject records for the present study. All data reported to Sanofi Pasteur by KPVSC will be deidentified and aggregated.

12.4 Monitoring, Auditing, and Archiving

12.4.1 Monitoring

Not applicable.

12.4.2 Audits and Inspections

The KPVSC has been using essentially the same system to manage data since 1985. Data management for data-only studies are performed by KPVSC almost entirely using the SAS system. Programs to manage data are used repeatedly, updating the SAS code as needed for protocol adherence.

Many utility macros have been created and maintained for use with the VSC data management programs. These stored compiled macros are available to KPVSC Data Analysts / Programmers for their use in constructing and testing programs.

Changes made to programs after the start of a study are documented as notes in the header/margin of the program or in the appropriate revision control system. Changes are applied only to copies of programs, and the original source is retained indefinitely. It is incumbent upon the Data Analyst / Programmer in charge of a particular task to document all programs and work performed; this includes code used as well as logs and listings produced.

Programming for vaccine studies at the KPVSC adheres to standards across all projects to ensure the preservation of code, logs, and listings, as well as good programming in data processing and transparency in methodology.

12.4.3 Archiving

KPNC databases created from KPNC EMRs are available for research purposes to KPVSC Data Analysts / Programmers for the duration that the project is open/approved by the KPNC IRB. Once the study is closed, the data are archived for future reference and regulatory compliance.

12.5 Financial Contract and Insurance Coverage

Not applicable.

12.6 Stipends for Participation

Not applicable.

By age group (or chronic disease status) and outcome
2-sided alpha=0.05 (likelihood ratio chi-sq test for superiority)
800,000 vaccinees expected per yr: 400K fluBlok v. 400K comparators

age=18-64 outcome=flu, test+

row	N expectd 3 yrs FluBlok	N expectd 3 yrs Comprtr	proportion of comparators who have the outcome	RR = 1 minus relative VE	Relative VE: % of breakthru cases prevented	Power (prob. of rejecting Ho if rel_VE is true)
1	1,200,000	1,200,000	0.00218	0.70	0.30	>.99
2	1,200,000	1,200,000	0.00218	0.75	0.25	>.99
3	1,200,000	1,200,000	0.00218	0.80	0.20	>.99
4	1,200,000	1,200,000	0.00218	0.85	0.15	>.99
5	1,200,000	1,200,000	0.00218	0.90	0.10	0.96
6	1,200,000	1,200,000	0.00218	0.95	0.05	0.45

age=18-64 outcome=hosp, flutest+

row	N expectd 3 yrs FluBlok	N expectd 3 yrs Comprtr	proportion of comparators who have the outcome	RR = 1 minus relative VE	Relative VE: % of breakthru cases prevented	Power (prob. of rejecting Ho if rel_VE is true)
7	1,200,000	1,200,000	0.00089	0.70	0.30	>.99
8	1,200,000	1,200,000	0.00089	0.75	0.25	>.99
9	1,200,000	1,200,000	0.00089	0.80	0.20	>.99
10	1,200,000	1,200,000	0.00089	0.85	0.15	0.95
11	1,200,000	1,200,000	0.00089	0.90	0.10	0.66
12	1,200,000	1,200,000	0.00089	0.95	0.05	0.22

Power of 3-yr study comparing FluBlok v Comparators
Power to detect relative VE against 5 types of outcome events
By age group (or chronic disease status) and outcome
2-sided alpha=0.05 (likelihood ratio chi-sq test for superiority)
800,000 vaccinees expected per yr: 400K fluBlok v. 400K comparators

age=18-49 outcome=flu, test+

row	N expectd 3 yrs FluBlok	N expectd 3 yrs Comprtr	proportion of comparators who have the outcome	RR = 1 minus relative VE	Relative VE: % of breakthru cases prevented	Power (prob. of rejecting Ho if rel_VE is true)
13	680,301	680,301	0.00229	0.70	0.30	>.99
14	680,301	680,301	0.00229	0.75	0.25	>.99
15	680,301	680,301	0.00229	0.80	0.20	>.99
16	680,301	680,301	0.00229	0.85	0.15	>.99
17	680,301	680,301	0.00229	0.90	0.10	0.82
18	680,301	680,301	0.00229	0.95	0.05	0.29

age=18-49 outcome=hosp, flutest+

row	N expectd 3 yrs FluBlok	N expectd 3 yrs Comprtr	proportion of comparators who have the outcome	RR = 1 minus relative VE	Relative VE: % of breakthru cases prevented	Power (prob. of rejecting Ho if rel_VE is true)
19	680,301	680,301	0.00065	0.70	0.30	>.99
20	680,301	680,301	0.00065	0.75	0.25	0.98
21	680,301	680,301	0.00065	0.80	0.20	0.88
22	680,301	680,301	0.00065	0.85	0.15	0.64
23	680,301	680,301	0.00065	0.90	0.10	0.33
24	680,301	680,301	0.00065	0.95	0.05	0.12

Power of 3-yr study comparing FluBlok v Comparators
Power to detect relative VE against 5 types of outcome events
By age group (or chronic disease status) and outcome
2-sided alpha=0.05 (likelihood ratio chi-sq test for superiority)
800,000 vaccinees expected per yr: 400K fluBlok v. 400K comparators

age=50-64 outcome=flu, test+

row	N expectd 3 yrs FluBlok	N expectd 3 yrs Comprtr	proportion of comparators who have the outcome	RR = 1 minus relative VE	Relative VE: % of breakthru cases prevented	Power (prob. of rejecting Ho if rel_VE is true)
25	519,699	519,699	0.00205	0.70	0.30	>.99
26	519,699	519,699	0.00205	0.75	0.25	>.99
27	519,699	519,699	0.00205	0.80	0.20	>.99
28	519,699	519,699	0.00205	0.85	0.15	0.95
29	519,699	519,699	0.00205	0.90	0.10	0.66
30	519,699	519,699	0.00205	0.95	0.05	0.22

age=50-64 outcome=hosp, flutest+

row	N expectd 3 yrs FluBlok	N expectd 3 yrs Comprtr	proportion of comparators who have the outcome	RR = 1 minus relative VE	Relative VE: % of breakthru cases prevented	Power (prob. of rejecting Ho if rel_VE is true)
31	519,699	519,699	0.00120	0.70	0.30	>.99
32	519,699	519,699	0.00120	0.75	0.25	>.99
33	519,699	519,699	0.00120	0.80	0.20	0.96
34	519,699	519,699	0.00120	0.85	0.15	0.79
35	519,699	519,699	0.00120	0.90	0.10	0.44
36	519,699	519,699	0.00120	0.95	0.05	0.15

age=50-64 outcome=PneumoniaHosp,Dec-March

row	N expectd 3 yrs FluBlok	N expectd 3 yrs Comprtr	proportion of comparators who have the outcome	RR = 1 minus relative VE	Relative VE: % of breakthru cases prevented	Power (prob. of rejecting Ho if rel_VE is true)
37	519,699	519,699	0.00248	0.70	0.30	>.99
38	519,699	519,699	0.00248	0.75	0.25	>.99
39	519,699	519,699	0.00248	0.80	0.20	>.99
40	519,699	519,699	0.00248	0.85	0.15	0.98
41	519,699	519,699	0.00248	0.90	0.10	0.74
42	519,699	519,699	0.00248	0.95	0.05	0.25

Power of 3-yr study comparing FluBlok v Comparators
Power to detect relative VE against 5 types of outcome events
By age group (or chronic disease status) and outcome
2-sided alpha=0.05 (likelihood ratio chi-sq test for superiority)
800,000 vaccinees expected per yr: 400K fluBlok v. 400K comparators

age=50-64 outcome=CVD hosp, Dec-March

row	N expectd 3 yrs FluBlok	N expectd 3 yrs Comprtr	proportion of comparators who have the outcome	RR = 1 minus relative VE	Relative VE: % of breakthru cases prevented	Power (prob. of rejecting Ho if rel_VE is true)
43	519,699	519,699	0.00620	0.70	0.30	>.99
44	519,699	519,699	0.00620	0.75	0.25	>.99
45	519,699	519,699	0.00620	0.80	0.20	>.99
46	519,699	519,699	0.00620	0.85	0.15	>.99
47	519,699	519,699	0.00620	0.90	0.10	0.99
48	519,699	519,699	0.00620	0.95	0.05	0.53

age=50-64 outcome=all hosp, Dec-March

row	N expectd 3 yrs FluBlok	N expectd 3 yrs Comprtr	proportion of comparators who have the outcome	RR = 1 minus relative VE	Relative VE: % of breakthru cases prevented	Power (prob. of rejecting Ho if rel_VE is true)
49	519,699	519,699	0.05000	0.70	0.30	>.99
50	519,699	519,699	0.05000	0.75	0.25	>.99
51	519,699	519,699	0.05000	0.80	0.20	>.99
52	519,699	519,699	0.05000	0.85	0.15	>.99
53	519,699	519,699	0.05000	0.90	0.10	>.99
54	519,699	519,699	0.05000	0.95	0.05	>.99

Power of 3-yr study comparing FluBlok v Comparators
Power to detect relative VE against 5 types of outcome events
By age group (or chronic disease status) and outcome
2-sided alpha=0.05 (likelihood ratio chi-sq test for superiority)
800,000 vaccinees expected per yr: 400K fluBlok v. 400K comparators
age=ChronicDis,50-64 outcome=flu, test+

row	N expectd 3 yrs FluBlok	N expectd 3 yrs Comprtr	proportion of comparators who have the outcome	RR = 1 minus relative VE	Relative VE: % of breakthru cases prevented	Power (prob. of rejecting Ho if rel_VE is true)
55	103,940	103,940	0.00286	0.70	0.30	0.98
56	103,940	103,940	0.00286	0.75	0.25	0.9
57	103,940	103,940	0.00286	0.80	0.20	0.73
58	103,940	103,940	0.00286	0.85	0.15	0.48
59	103,940	103,940	0.00286	0.90	0.10	0.24
60	103,940	103,940	0.00286	0.95	0.05	0.09

age=ChronicDis,50-64 outcome=hosp, flutest+

row	N expectd 3 yrs FluBlok	N expectd 3 yrs Comprtr	proportion of comparators who have the outcome	RR = 1 minus relative VE	Relative VE: % of breakthru cases prevented	Power (prob. of rejecting Ho if rel_VE is true)
61	103,940	103,940	0.00200	0.70	0.30	0.91
62	103,940	103,940	0.00200	0.75	0.25	0.78
63	103,940	103,940	0.00200	0.80	0.20	0.58
64	103,940	103,940	0.00200	0.85	0.15	0.36
65	103,940	103,940	0.00200	0.90	0.10	0.18
66	103,940	103,940	0.00200	0.95	0.05	0.08

age=ChronicDis,50-64 outcome=PneumoniaHosp,Dec-March

row	N expectd 3 yrs FluBlok	N expectd 3 yrs Comprtr	proportion of comparators who have the outcome	RR = 1 minus relative VE	Relative VE: % of breakthru cases prevented	Power (prob. of rejecting Ho if rel_VE is true)
67	103,940	103,940	0.00744	0.70	0.30	>.99
68	103,940	103,940	0.00744	0.75	0.25	>.99
69	103,940	103,940	0.00744	0.80	0.20	0.99
70	103,940	103,940	0.00744	0.85	0.15	0.87
71	103,940	103,940	0.00744	0.90	0.10	0.53
72	103,940	103,940	0.00744	0.95	0.05	0.17

Power of 3-yr study comparing FluBlok v Comparators
Power to detect relative VE against 5 types of outcome events
By age group (or chronic disease status) and outcome
2-sided alpha=0.05 (likelihood ratio chi-sq test for superiority)
800,000 vaccinees expected per yr: 400K fluBlok v. 400K comparators

age=ChronicDis,50-64 outcome=CVD hosp, Dec-March

row	N expectd 3 yrs FluBlok	N expectd 3 yrs Comptr	proportion of comparators who have the outcome	RR = 1 minus relative VE	Relative VE: % of breakthru cases prevented	Power (prob. of rejecting Ho if rel_VE is true)
73	103,940	103,940	0.01860	0.70	0.30	>.99
74	103,940	103,940	0.01860	0.75	0.25	>.99
75	103,940	103,940	0.01860	0.80	0.20	>.99
76	103,940	103,940	0.01860	0.85	0.15	>.99
77	103,940	103,940	0.01860	0.90	0.10	0.9
78	103,940	103,940	0.01860	0.95	0.05	0.36

age=ChronicDis,50-64 outcome=all hosp, Dec-March

row	N expectd 3 yrs FluBlok	N expectd 3 yrs Comptr	proportion of comparators who have the outcome	RR = 1 minus relative VE	Relative VE: % of breakthru cases prevented	Power (prob. of rejecting Ho if rel_VE is true)
79	103,940	103,940	0.10000	0.70	0.30	>.99
80	103,940	103,940	0.10000	0.75	0.25	>.99
81	103,940	103,940	0.10000	0.80	0.20	>.99
82	103,940	103,940	0.10000	0.85	0.15	>.99
83	103,940	103,940	0.10000	0.90	0.10	>.99
84	103,940	103,940	0.10000	0.95	0.05	0.97

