2.2 Secondary Objectives

Among all adults 50–64 years who receive either Flublok Quadrivalent or SD-IIV during the 2018–2019, 2019–2020, and/or 2020–2021 influenza seasons, we will estimate the rVE of Flublok Quadrivalent vaccine versus SD-IIV against the following outcomes:

- PCR-confirmed hospitalized influenza
- Hospitalized community-acquired pneumonia (CAP) (we will only include primary diagnoses for this outcome)
- Hospitalized cardio-respiratory events combined (e.g., CAP, other lower respiratory tract infections [LRTI], acute myocardial infarction, congestive heart failure, stroke, atrial fibrillation) (we will only include primary diagnoses for this outcome)
- All PCR-confirmed influenza A
- All PCR-confirmed influenza B

For these 5 secondary objectives, adjustment for multiplicity will be applied.

Sub-analyses of *primary* outcome in sub-groups defined by pre-existing conditions (listed below) will also be conducted among adults 50–64 years. Additionally, sub-analyses of *secondary*

outcomes of sub-groups defined by pre-existing conditions will be conducted as feasible among adults 50–64 years.

“Pre-existing” will be defined as history of a condition in the 3 years prior to vaccination date.

- i. **Cardiovascular preexisting conditions composite, which may include:** myocardial infarction, cerebrovascular accident, atrial fibrillation, arrhythmias, coronary artery disease, valvular heart disease/valvuloplasty, chronic/congestive heart failure and/or congenital heart defects, CABG, angioplasty/stents, cardioversion, pacemaker, implantable cardioverter defibrillator, LVAD, heart transplant, hypertensive disease
- ii. **Respiratory preexisting conditions composite, which may include:** COPD and/or pulmonary HTN
- iii. **Cardiorespiratory preexisting conditions composite:** combined pre-existing conditions (a) and (b) above
- iv. **Obesity:** based on available height/weight data for a calculated BMI ≥ 30 or an obesity diagnosis (e.g., ICD-10 E66.9)
- v. **Diabetes:** based on a diagnosis of diabetes

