4.2 Secondary Endpoints and Assessment Methods

For each of the secondary outcomes listed below, we will count the first event of the outcome per influenza season and censor follow-up after the first event. The influenza season is defined as the first day that KPNC begins use of the Cepheid GeneXpert PCR assay for the influenza season (generally the first Tuesday of October); the end of the season is generally determined when the proportion of influenza-positive PCR tests drops below 10%, or the first week of May, whichever is later.

For all secondary objectives excluding the sub-analyses by pre-existing conditions, adjustment for multiplicity will be applied following the Holm adjustment method¹:

1. We will rank order the 5 p-values obtained from tests of the 5 null hypotheses about rVE with respect to each of the 5 secondary outcomes listed above.
2. The 5 p-values will be ranked in order from the smallest p-value to the largest: $p_{(01)} \leq p_{(02)} \leq p_{(03)} \leq p_{(04)} \leq p_{(05)}$
3. The corresponding alpha critical values to determine significance are to be used based on rank:
 - i. $\alpha_{(C_01)} = \alpha/5 = 0.0100$
 - ii. $\alpha_{(C_02)} = \alpha/4 = 0.0125$
 - iii. $\alpha_{(C_03)} = \alpha/3 = 0.0167$
 - iv. $\alpha_{(C_04)} = \alpha/2 = 0.0250$
 - v. $\alpha_{(C_05)} = \alpha/1 = 0.0500$

The 5 hypothesis tests will be done sequentially in the order given above, until one of the p-values is found to be higher than the corresponding critical value. If the lowest p-value is below 0.01, we

will reject the corresponding null hypothesis, and proceed to the next-lowest p-value. If, and only if, both the 1st and 2nd p-values are below their corresponding critical values, we will proceed to the 3rd lowest p-value. We will test the 5 secondary hypotheses sequentially in this way, comparing the next p-value to its critical value only if all of the lower p-values were below their corresponding critical values.

[figure not shown]
Among all adults 50–64 years who receive either Flublok Quadrivalent or SD-IIV during the 2018–2019, 2019–2020, and/or 2020–2021 influenza seasons, we will estimate the rVE of Flublok Quadrivalent vaccine versus SD-IIV against the following outcomes:

- PCR-confirmed hospitalized influenza

Among adults aged 50–64 years who are vaccinated with Flublok or an SD-IIV, we plan to assess the number of adults who have a PCR-positive test during the influenza season ≥ 14 days after vaccination and are hospitalized.

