5.1 Statistical Methods

5.1.1 Hypotheses and Statistical Methods for Primary, Secondary, and Exploratory Objectives

5.1.1.1 Hypotheses

For the primary objective, we plan to test the null hypothesis that there is no difference in effectiveness between Flublok and SD-IIV. We will use a 2-sided test ($p<0.05$) with an associated 95% confidence interval to assess superiority. The same null hypothesis of no difference in effectiveness will be tested for all secondary objectives. Analyses in subgroups defined by pre-existing conditions will not adjust for multiplicity; all other secondary analyses will adjust for multiplicity by the Holm method specified in Section 4.2.

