5.3 Determination of Sample Size and Power Calculation

We calculated the least rVE that is detectable with 80% power in a 3-year study for several aims. We plan to test the null hypothesis that Flublok is not any more or less effective than the comparator, using a 2-sided test, $p<0.05$. Our allocation ratio of 1:1 implies that each year, KPNC would give Flublok Quadrivalent vaccine to 400,000 members aged 18–64 years, and SD-IIV to another 400,000 similar KPNC members.

Because the comparison group will not be unvaccinated—they are getting SD-IIV—we will be estimating and testing rVE: i.e., the percent reduction in the incidence of “breakthrough cases” (e.g., influenza episodes in vaccinees) that results from the use of Flublok Quadrivalent vaccine rather than the SD-IIV vaccines.

We may potentially conduct analyses of rVE within subgroups and periods of time defined by:

- Time-since-vaccination: number of days, counting from Day 15 after vaccination (where day 0 is the day of vaccination)
- Time-since-beginning-of-the-season
- Season: Year 1 or Year 2
- Comorbidities: Diagnostic cost groups (DxCG) risk scores from the ICD-based proprietary risk adjustment and predictive modeling system may be used. DxCG calculates projected healthcare costs for each member for the upcoming year based on demographics, diagnoses, costs, and utilization in the previous year. It may also be included as a proxy for overall health status of the individual.
- Prior healthcare utilization (e.g., number of emergency department visits or hospitalizations in prior year, outpatient visits in prior year)
- Influenza vaccine type received (or none) during the previous year

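### At the tabulated incidence, the stated power for PCR-confirmed hospitalised influenza at ages 50–64 (rows 31–36) is an upper bound, because the SAP tests this outcome under Holm

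*Protocol*

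**What the plan says.** **Power.** Each block of power tables in Protocol Section 15 carries the line "2-sided alpha=0.05 (likelihood ratio chi-sq test for superiority". Rows 31–36, labelled "age=50-64 outcome=hosp, flutest" positive, use 519,699 vaccinees per arm and a comparator incidence of 0.00120. The stated power is >.99, >.99, 0.96, 0.79, 0.44 and 0.15 for rVE of 30, 25, 20, 15, 10 and 5%. Protocol 11.2 gives the same two-sided 0.05 level. SAP 5.3 says "We calculated the least rVE that is detectable with 80% power in a 3-year study for several aims" and continues "We plan to test the null hypothesis that Flublok is not any more or less effective than the comparator", again with a two-sided test at p<0.05. It does not mention multiplicity.

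**Test.** SAP 2.2 lists PCR-confirmed hospitalised influenza at ages 50–64 first among five secondary outcomes and adds: "For these 5 secondary objectives, adjustment for multiplicity will be applied". SAP 4.2 sets out the Holm steps: "The corresponding alpha critical values to determine significance are to be used based on rank", namely 0.0100, 0.0125, 0.0167, 0.0250 and 0.0500. SAP 5.1.1.1 exempts only the pre-existing-condition subgroups; "all other secondary analyses will adjust for multiplicity by the Holm method specified in Section 4.2".

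**The concern.** The SAP sets one rule for declaring a secondary outcome significant and describes power under another. The plan's own yardstick is the smallest rVE detectable with 80% power. A reader looking up hospitalised influenza finds row 34 (power 0.79) and concludes that about 15% is detectable. Under Holm, significance for this outcome can require a p-value as low as 0.01, depending on how the other four outcomes turn out. If the true rVE is about 20% or less, a non-significant result could then be taken as stronger evidence against a useful effect than it is.

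This is a mismatch between stated power and planned test. Enrolment, control of the error rate and the primary analysis are not at stake.

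**Working it through.** **Inputs.** N = 519,699 per arm, comparator proportion p₁ = 0.00120 and p₂ = p₁(1 − rVE), from rows 31–36; two-sided alpha 0.05 and the likelihood-ratio chi-square, from the table header; Holm critical values from SAP 4.2.

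**Formula.** With p̄ = (p₁ + p₂)/2, the noncentrality is λ = 2N Σᵢ [pᵢ ln(pᵢ/p̄) + (1 − pᵢ) ln((1 − pᵢ)/(1 − p̄))]. Power ≈ Φ(√λ − z), with z = 1.960 at alpha 0.05 and 2.576 at alpha 0.01; the opposite tail matters only at the smallest rVE and is included in the table.

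**Row 34 in full (rVE 15%).**
- Expected events: 519,699 × 0.00120 = 623.6 (comparator) and 623.6 × 0.85 = 530.1 (Flublok).
- Event terms of λ: 2 × [623.6 × ln(1/0.925) + 530.1 × ln(0.85/0.925)] = 2 × (48.62 − 44.82) ≈ 7.6. With the non-event terms, λ = 7.60 and √λ = 2.757.
- Alpha 0.05: Φ(2.757 − 1.960) = Φ(0.797) = 0.79, the stated value.
- Alpha 0.01: Φ(2.757 − 2.576) = Φ(0.181) = 0.57.

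**All six rows.**

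| Row | rVE | λ | Stated | Alpha 0.05 | Alpha 0.01 |
|---|---|---|---|---|---|
| 31 | 30% | 33.22 | >.99 | >0.99 | >0.99 |
| 32 | 25% | 22.37 | >.99 | >0.99 | 0.98 |
| 33 | 20% | 13.90 | 0.96 | 0.96 | 0.88 |
| 34 | 15% | 7.60 | 0.79 | 0.79 | 0.57 |
| 35 | 10% | 3.29 | 0.44 | 0.44 | 0.22 |
| 36 | 5% | 0.80 | 0.15 | 0.15 | 0.05 |

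The stated figures reproduce at alpha 0.05.

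**Why the last two columns bound Holm power.** With five hypotheses, a p-value below 0.01 is always rejected: every smaller p-value also passes its step, and later thresholds are larger. A p-value above 0.05 is never rejected. So, at fixed N and incidence, Holm power for this outcome lies between the two columns, whatever the effects on the other outcomes or the correlations.

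**rVE detectable with 80% power.** Solving √λ = z + 0.842 at p₁ = 0.00120:

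| Critical value | 0.05 | 0.025 | 0.0167 | 0.0125 | 0.01 |
|---|---|---|---|---|---|
| Detectable rVE | 15.2% | 16.7% | 17.5% | 18.0% | 18.4% |

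**Where in the range.** This needs assumptions that the documents do not supply. One simulation of the full procedure (400,000 trials per scenario) took hospitalised cases as a subset of PCR-positive cases (0.00205), a stand-in incidence for the cardio-respiratory composite of 0.00248 + 0.00620 = 0.00868, and an influenza A share of 60–90%. If all five outcomes share the same rVE, power is about 0.94, 0.69 and 0.30 at rVE 20, 15 and 10%, and the detectable rVE is 16.6–16.7%. With no effect on pneumonia or cardiovascular events, power is about 0.89, 0.60 and 0.24, and the detectable rVE is 18.0%. These figures illustrate; the bounds do not depend on them.

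**The case against.** **The table prints its alpha, and the protocol plans no Holm adjustment.** Both are true, so this is not an arithmetic error, and the table agrees with the protocol's own 0.05 test. But SAP 5.3 repeats p<0.05 in the same document that sets the Holm rule, and gives no qualification.

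**The incidence is uncertain, and that matters more than Holm.** This stands and limits the claim. By calculation, an incidence 1.5 times the tabulated one (0.0018) gives power 0.79 at rVE 15% even at alpha 0.01. In the other direction, 0.00120/0.00205 implies that 59% of PCR-positive cases at these ages are hospitalised. Protocol 8.1.1 says that only a very small part of influenza cases are admitted, though not specifically for this age group. If the share were 20% (an assumption; incidence 0.00041), the detectable rVE would be about 25% at alpha 0.05; at 10% it would be about 35%. Both shifts exceed the Holm effect. The corrected range must therefore be tied to 0.00120.

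**The practical loss is small.** It is at rVE of 25% or more, where power is at least 0.98 throughout. The 30–43% in Protocol 1.2 concerned laboratory-confirmed influenza-like illness at ages 50 and over, not hospitalised influenza, and the plan itself tabulates rVE down to 5%.

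**Stronger readings that a reader might infer.** One is that the alpha 0.01 column is the planned power. It is only the floor, since Holm relaxes the threshold as other outcomes are rejected. Another is that the same bound applies to the pneumonia rows (37–42, "age=50-64 outcome=PneumoniaHosp,Dec-March") and the CVD rows (43–48). The documents do not support this. SAP community-acquired pneumonia has a longer window than December–March but counts primary diagnoses only, so its incidence could be higher or lower than the row's. CVD hospitalisation alone is not one of the five Holm outcomes.

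**Conclusion.** The point holds as a consistency error between stated power and planned test. At 519,699 per arm and incidence 0.00120, rows 31–36 overstate what the Holm procedure can be relied on to deliver: they are its ceiling. The shortfall from the stated value is at most 0.08 at rVE 20%, 0.22 at 15%, 0.22 at 10% and 0.10 at 5%. The detectable rVE moves from 15.2% to at most 18.4%.

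The bound rests on the tabulated N and incidence and on the likelihood-ratio approximation that the table names. It does not hold unconditionally: a sufficiently higher incidence of the SAP-defined outcome would restore the stated power. The primary outcome (rows 25–30) is outside the Holm family and unaffected. Nothing here calls the design or the error control into question.

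**What to change.** In SAP 5.3, add that the tabulated powers for secondary outcomes use an unadjusted two-sided alpha of 0.05 and do not reflect the Holm procedure in SAP 4.2. Restate rows 31–36 there as the range from alpha 0.01 to alpha 0.05: >0.99; 0.98 to >0.99; 0.88–0.96; 0.57–0.79; 0.22–0.44; 0.05–0.15. Give the matching detectable rVE at 80% power (18.4% to 15.2%), and mark the whole as conditional on the comparator incidence of 0.00120. Carry the same text into Protocol 11.2 and Section 15 at the next amendment. This point calls for no change to the other rows.

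The cost is a few sentences and one restated table block in the SAP. The protocol text needs the sponsor's written approval under Protocol 5.3, which is why it can wait for an amendment made for other reasons. Secondary power will look less favourable at rVE of about 20% or less. Enrolment and all tests stay as planned.
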